#### 14.6.3.1 Investigator Assessment of Wound Healing

The investigator will assess wound healing of target wounds (treated and control/untreated) based on the digital images of the target wounds. The investigator will assess wound healing of target wounds from 0% to 100% healed on a categorical scale. The wound healing assessment will be captured in the following categories.

- 0%
- 1-9%
- 10-24%

CONFIDENTIAL Page 61 of 75

Fibrocell Technologies RDEB Phase I/II Protocol Final Version 8.0, 29 Oct 2019

- 25-49%
- 50-74%
- 75-89%
- 90-99%
- 100%

## 14.7 Safety Analyses

All continuous parameters will be summarized using standard summary statistics as appropriate (n, mean, standard deviation, median, minimum, maximum, 25th percentile, and 75th percentile). Summary statistics for categorical variables will include frequency counts and percentages.

Patient demographics and relevant baseline data will be analyzed descriptively. Inclusion and exclusion criteria ensure that participants are suitable for the study. Premature termination will be tabulated and summarized.

#### 14.7.1 Adverse Events

Adverse events will be coded using the MedDRA adverse event dictionary. Safety evaluations will be based on occurred adverse events, laboratory values, vital signs and appearance of C7 antibodies, and RCL. Severities of toxicities will be described using the NCI Common Toxicity Criteria (CTC) grades.

Adverse events will be grouped into pre-treatment adverse events and treatment-emergent adverse events and will be tabulated by preferred terminology and by body system for each study phase. The number of adverse event entries, as well as the number of patients will be reported. Analyses will include tabulation of adverse event type, relationship to FCX-007, seriousness, and severity of adverse events according to CTCAE.

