# 3 Experimental Plan

### 3.1 Study Design

This is a Phase I/II Study of FCX-007 (Genetically-Modified Autologous Human Dermal Fibroblasts) for Recessive Dystrophic Epidermolysis Bullosa (RDEB) being conducted by Fibrocell to evaluate FCX-007 in subjects with RDEB. Up to twelve subjects will be enrolled, up to six (6) in Phase I, and up to six (6) in Phase II. Phase I will enroll adult subjects only; Phase II can enroll adults and pediatric subjects (aged seven (7) or older). Within Phase I, subjects will be assigned to one of two arms: subjects with NC1+ status will be enrolled into Arm A and subjects with NC1- status will be enrolled into Arm B. The arms will enroll independently. In Phase I, the study may enroll an equivalent number of subjects to Arm A and Arm B (n=3 each arm). In Phase II, the study will target enrolling 3 subjects to each arm, but will allow a disproportionate distribution of subjects between Arm A and Arm B to equal 6 total subjects.

Figure 2 - High-Level Study Design

One administration of FCX-007 will consist of up to sixty (60) 0.25 mL intradermal injections in wounded and/or intact skin. The majority of the injections will be administered around the margin of target wounds and at least 6 injections will be administered to intact skin. The Investigator will attempt to administer all 15mL of FCX-007. This will be accomplished by selecting target wounds that are as close as possible to 54 linear cm, leaving at least 6 administrations for intact skin, for a total of 60 injections.

For the wound administrations, subjects will receive FCX-007 administered intradermally to one, two or three paired target wounds at Visit 3 (Day 0). Subjects will receive a second administration to wounded and/or intact skin at Visit 5 (Week 4).

In this study, one wound in each target wound pair will be used as a control for efficacy and safety evaluations. FCX-007 administered wounds will be compared within paired target wounds to untreated wounds.

CONFIDENTIAL Page 17 of 75

Final Version 8.0, 29 Oct 2019

As there is no previous human experience with FCX-007, treatment administration will be staggered in two places:

- 1. Between the first and second enrolled subjects in each arm.
- 2. Between the third and fourth enrolled subjects in each arm.

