## 9.2 Treatment Assignment of Paired Wounds

Paired wounds will be randomly assigned to receive FCX-007 or no treatment.

On Visit 2, during the selection of the target wounds, each wound of up to three target wound pairs will be labeled by the investigator as T1A and T1B for the 1st pair, T2A and T2B for the 2nd pair, and T3A and T3B for the 3rd pair. Following the determination of target wound pairs, the Investigator will assign each wound to either active treatment or no treatment randomly.

CONFIDENTIAL Page 42 of 75

Fibrocell Technologies RDEB Phase I/II Protocol Final Version 8.0, 29 Oct 2019

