#### 13 **Adverse Experiences**

#### 13.1 Definitions

#### 13.1.1 Adverse Events

An Adverse Event (AE) is any untoward medical occurrence in a clinical investigation subject administered a pharmaceutical product and which does not necessarily have a causal relationship with this treatment. An AE can therefore be any unfavorable and unintended sign (including an abnormal laboratory finding), symptom, disease or exacerbation of a pre-existing condition temporally associated with the use of a medicinal (investigational) product.

Subjects should be asked a non-leading question in order to avoid bias in eliciting AEs; such as "How are you feeling?" It is important to question the subject in a non-leading way about changes in their health or concomitant medication usage since their last visit. Where possible, a diagnosis rather than a list of symptoms should be recorded. If a diagnosis has not been made then each symptom should be listed individually.

Each AE requires a complete description including date of onset and corrective actions taken. The intensity of the AE and its relationship to the investigational product, as well as its outcome, must be recorded in the CRF.

Symptoms of the disease under study/lack of efficacy should not be considered as AEs, as long as they are within the normal day-to-day fluctuation or expected progression of the disease. However, significant worsening of the symptoms should be recorded as an AE.

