A change in the value of a safety laboratory evaluation can represent an AE if the change is clinically relevant (as determined by the Investigator) or if, during treatment with the investigational product, a shift of a parameter is observed from a normal value to a pathological value, or a further worsening of an already pathological value. When evaluating such changes, the extent of deviation from the reference range, the duration until return to the reference range, either while continuing treatment or after the end of treatment with the investigational product, and the range of variation of the respective parameter within its reference range, should be taken into consideration. The Investigator should decide, based on the above criteria and the clinical condition of a subject, whether a change in a laboratory parameter represents an AE. For pathological laboratory values that were not present at baseline, follow-up laboratory evaluations should be performed until the values return to within reference range or until a plausible explanation is found.

AEs should be recorded, starting from subject enrollment (date of signature on informed consent) per the Schedule of Events, until the end of the Long Term Follow-Up Period, and are to be recorded on the appropriate AE pages in the CRF and in source documents. Where possible, all AEs should be followed to resolution, or an outcome is reached. Medical tests and examinations will be performed, as appropriate, to document resolution of event(s).

CONFIDENTIAL Page 55 of 75 Fibrocell Technologies RDEB Phase I/II Protocol Final Version 8.0, 29 Oct 2019

**NOTE:** Blistering MUST be noted as an AE if it is seen proximal to a product-treated wound.

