## 13.2 Reporting Procedures

All adverse events occurring after FCX-007 administration observed by the investigator or reported by the subject (whether or not attributed to investigational product), will be reported on the case report form.

Medically significant adverse events considered related to the investigational product by the investigator or the sponsor will be followed until resolved or considered stable. The investigator must assign the following attributes: description; dates of onset and resolution; severity; assessment of relatedness to investigational product, and action taken. The investigator may be asked to provide follow-up information.

All deaths occurring on study must be reported to Fibrocell. These include deaths during the Long-Term Follow-Up period. For all deaths, available autopsy reports and relevant medical reports should be provided to the Medical Monitor.

The investigator should notify the IRB of serious adverse events occurring at the site and other

CONFIDENTIAL Page 56 of 75

Fibrocell Technologies RDEB Phase I/II Protocol

Final Version 8.0, 29 Oct 2019

adverse event reports received from Fibrocell, in accordance with local procedures.

It will be left to the investigator's clinical judgment whether or not an adverse event is of sufficient severity to require the subject's removal from study. A subject may also voluntarily withdraw from study due to what he or she perceives as an intolerable adverse event. If either of these occurs, the subject will be asked to undergo an early termination assessment and be given appropriate care under medical supervision until symptoms cease or the condition becomes stable. If the subject was permanently withdrawn from the study due to a serious adverse event, this information must be included in either the initial or follow-up Serious Adverse Event Report Form, and in the End of Study Case Report Form.

The severity of toxicities will be assessed on the following scale with appropriate clinical definitions: Grade1 = mild adverse event, Grade2 = moderate adverse event, Grade3 = severe adverse event, Grade4 = immediate life threatening adverse event, and Grade5 = fatal adverse event.

The relationship of adverse events to the investigational product will be assessed by the investigator using good clinical judgment according to the following definitions:

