#### 13.2.1 Post-FCX-007 Administration Adverse Event Monitoring

The Investigator must monitor the subject's wounds closely for additional blister formation and expansion of the border of the wound during injections and immediately post-administration up to the 2 day follow up visit. Additional blister formation and/or expansion of the border of the wound must be recorded as an adverse event.

CONFIDENTIAL Page 57 of 75

Fibrocell Technologies RDEB Phase I/II Protocol Final Version 8.0, 29 Oct 2019

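### The untreated wound is declared a safety control, but local adverse events need carry no wound identifier and no treated-versus-control table is planned for them

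*Combined protocol and SAP*

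**What the plan says.** Safety is the sole primary objective (Section 2.2.1). Section 3.1, like the synopsis, states that "one wound in each target wound pair will be used as a control for efficacy and safety evaluations". Section 9.2 adds: "Paired wounds will be randomly assigned to receive FCX-007 or no treatment". The subject-level arms are not randomised: "subjects with NC1+ status will be enrolled into Arm A and subjects with NC1- status will be enrolled into Arm B".

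Two places list what is recorded for an adverse event. Section 13.1.1: "Each AE requires a complete description including date of onset and corrective actions taken". Section 13.2: "The investigator must assign the following attributes: description; dates of onset and resolution; severity; assessment of relatedness to investigational product, and action taken". Section 13.1.1 also asks for intensity, relationship to product and outcome.

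Two rules govern local events. Section 13.1.1: "Blistering MUST be noted as an AE if it is seen proximal to a product-treated wound". Section 13.2.1, covering the period up to the two-day visit: "Additional blister formation and/or expansion of the border of the wound must be recorded as an adverse event".

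Section 14.7.1 tabulates events by coded term and body system within each phase, with relationship, seriousness and severity. Its counting rule is: "The number of adverse event entries, as well as the number of patients will be reported".

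Section 14.2 sets a general rule. Summaries are by treatment regimen, discrete variables may be counted by subject or by wound, and treatment comparisons allow for pairing where that applies. Section 14.6.3 compares area, healing and closure of treated and control wounds, as proof of mechanism.

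**The concern.** The wound pair is the only randomised contrast in the trial, and the protocol says it serves safety. For local events such as infection, blistering, border expansion, pain and skin cancer near a target wound, the obvious use is to ask whether they occur more often at the treated wound than at its untreated partner. Section 14.7.1 neither asks that question nor counts in a unit that could answer it, and the required event attributes do not supply the missing label.

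This matters because the background rate of such events is high. Section 11.1.1 itself notes the raised risk of serious events, including serious infections, in this disease. Without the paired display, telling product effect from disease for most local events rests on the investigator's relatedness rating. That investigator also assigns the wounds (9.2), control wounds receive nothing, and the documents describe no masking of the rating.

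**Working it through.** The plan gives no sample size calculation (14.1) and no event rates, so there is no stated figure to reproduce. The check is a comparison of sections, followed by arithmetic for scale.

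**1. What the declared comparison needs, and what is provided.**
- A label tying each local event to the treated wound, the control wound or another site. Neither attribute list (13.1.1, 13.2) requires one.
- A table by treated and control wound. None is named anywhere in 14.7. Section 14.6, by contrast, repeatedly specifies comparison between treatments.
- Equal recording at both wounds. The blistering rule in 13.1.1 names only product-treated wounds. The rule in 13.2.1 does not say whether it covers control wounds.

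Other rules already depend on location. The fifth suspension trigger in 11.1.1 concerns infection in a product-treated wound, and sampling of skin cancers (7.5.1, 11.4) depends on the injected region.

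**2. Whether 14.2 fills the gap.** The safety population is everyone given FCX-007 (14.4.1), and each of these subjects also has a control wound. A subject-level table by treatment therefore has no untreated column. Counting by wound would supply one, but needs the label that is not required.

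**3. What the planned counts can show.** Assume one pair per subject, 12 subjects, independence between the two wounds, and one entry per affected wound. Let t and c be the event rates at treated and control wounds.

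Share of patients with an event = 1 − (1 − t)(1 − c). Expected entries = 12(t + c).

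| t | c | Patients with an event | Expected entries |
|---|---|---|---|
| 0.50 | 0.10 | 1 − 0.50 × 0.90 = 55% | 12 × 0.60 = 7.2 |
| 0.10 | 0.50 | 1 − 0.90 × 0.50 = 55% | 12 × 0.60 = 7.2 |
| 0.33 | 0.33 | 1 − 0.67 × 0.67 = 55% | 12 × 0.66 = 7.9 |

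Both counts are unchanged when t and c are swapped, so neither can tell harm from benefit. That symmetry does not depend on the assumed rates or on independence; the 55% does.

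**4. Size of the paired table.** With one to three pairs per subject (3.1) there are 12 × 1 = 12 to 12 × 3 = 36 pairs at full enrolment. With the optional seventh Phase II subject (3.3) there are 13 to 39. Under an exact McNemar test, d discordant pairs all in one direction give two-sided p = 2 × 0.5^d. Five give 0.0625 and six give 0.031, so at least six are needed at the 0.05 level of 14.2.

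Power to detect excess at the treated wound, for assumed rates and independent wounds:

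| Treated / control | 12 pairs | 36 pairs |
|---|---|---|
| 0.30 / 0.10 | 4% | 45% |
| 0.60 / 0.30 | 15% | 65% |
| 0.50 / 0.10 | 32% | 95% |
| 0.70 / 0.10 | 74% | over 99% |

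The 36-pair column ignores clustering of pairs within subjects and is optimistic.

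**The case against.** Four stronger readings are tempting, and the documents do not support them.

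- A reader might infer that events are tabulated by patient only. Section 14.7.1 also counts entries. What is missing is a count by wound.
- A reader might infer that the comparison can never be made. Section 14.2 gives a general by-treatment and paired rule, 14.7.1 does not exclude further tables, and 14.6.3 compares wound dimensions between treated and control wounds. Border expansion would thus show partly as enlargement. Infection, pain and carcinoma would not.
- A reader might infer that events carry no location at all. The case report form is not in the documents, and the required free-text description may well mention a site. Optional text is still not a dependable analysis variable.
- A reader might infer that the wound pair is the only way to separate product from disease without a causality judgment. Section 11.1.1 provides vector testing of skin cancers and refers to product sterility results for infection of treated wounds. These tests bear on particular events and do not replace a comparison of frequency.

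It is also fair that this is a pilot with exploratory analyses, and that systemic events, RCL and serum C7 antibodies cannot be assigned to a wound. Much of the primary safety objective is therefore untouched.

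The most important objection concerns the remedy. A by-wound table added alone would be biased against the product, because blistering is a mandatory event only near treated wounds. Some events may also belong to no single wound, since paired wounds may be close together (9.1.1) and a treated region may be part of a larger wound (9.1). Both objections stand, and the fix has to meet them.

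**Conclusion.** The point holds for local adverse events. The protocol declares a randomised within-pair safety control, but following Sections 13 and 14.7.1 as written does not deliver that comparison, and Section 14.2 cannot reliably supply it without a required site identifier. The conclusion rests on the listed attributes and tabulations, and would soften if the case report form already has a site field.

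The loss is one of description, not of a powered test. With so few pairs a clear paired display is the most that can be expected, but it bears directly on the primary objective. All event rates used for scale are assumptions.

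**What to change.** 1. **Event site.** Add a site field to the adverse event form for local events: wound label T1A to T3B, intact-skin injection site, biopsy site, elsewhere, and a category for events that cannot be assigned to one wound (adjacent or partial wounds). Back-code earlier events from their descriptions where possible.
2. **Equal recording.** Apply the same recording rule for local events to both wounds of each pair, including blistering (13.1.1) and border expansion (13.2.1). Flag events recorded before the change as unequally ascertained.
3. **Table.** Add to 14.7.1 a descriptive paired table of local events: pairs with the event at the treated wound only, the control wound only, both and neither, regardless of relatedness rating. List events at intact-skin sites separately. State that the table is descriptive.

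The cost is one form field, one table and some back-coding, with no new visits or procedures. Location data will stay incomplete for subjects already dosed, and equal recording cannot be restored for them.

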Safety is monitored throughout the study, captured during on-site visits and while the subject is off-site through adverse event diaries. The following assessments in each subject will be assessed: adverse events (AEs), physical examinations, vital signs, clinical laboratory evaluations (including C7 antibodies, and RCL), medical history, and prior/concomitant medications, as appropriate. A DSMB will periodically review subject safety data.

The Long-Term Follow-Up is a 15-year period following Week 52/ET in which safety is monitored (including RCL testing yearly and any new malignancies to 15-years) at a minimum annually. If all post-treatment RCL assays are negative during the first year (e.g., Weeks 4, 12, 16, 25, 32, and 52), collection of the yearly follow-up samples will be discontinued.

CONFIDENTIAL Page 9 of 75

Final Version 8.0, 29 Oct 2019

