#### Safety Evaluations

Safety will be monitored throughout the study. The following assessments in each subject will be assessed: adverse events (AEs), physical examinations, vital signs, clinical laboratory evaluations, medical history, and prior/concomitant medications. Specifically, the following will be assessed for adverse events:

- Changes in laboratory values, including:
  - C7 Antibodies as assayed by linear basement membrane zone (BMZ) staining for IgM, IgG, IgA or serum IgG antibodies binding to the epithelium of monkey esophagus with a basement membrane or superficial dermal pattern by indirect immunofluorescence (IIF) microscopy
  - Direct immunofluorescence (DIF) of subject's skin biopsy staining for IgM, IgG, IgA or complement staining in a linear BMZ distribution localizing to the dermal-epidermal junction
  - Replication Competent Lentivirus (RCL)
  - Complete Blood Count with Differential
- Changes in vital signs: blood pressure, heart rate, respiratory rate, temperature
- Change in physical exam
- Long-term safety follow-up including:
  - Delayed adverse events for at least 15 years in which safety is monitored at a minimum annually.
  - Replication Competent Lentivirus evaluation yearly for up to 15 years. If all post-treatment assays are negative during the first year (e.g., Weeks 4, 12, 16, 25, 32, and 52), collection of the yearly follow-up samples will be discontinued.
  - Any new malignancies to Year 15

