Persistent blistering begins at birth and contributes to the high mortality risk due to bacterial infection. In a study of 41 RDEB patients, the infectious causes of pneumonia and sepsis resulted in death in 14.6% and 9.8% respectively (Fine, 2010). Patients who survive bacterial sepsis during early infancy are at a high risk of later developing more severe complications such as growth retardation due to gastrointestinal involvement (Fine, 2008), multifactorial anemia, esophageal strictures, corneal scarring and/or progressive blindness (Fine, 2004), post streptococcal glomerulonephritis, renal failure, progressive hand and foot deformities such as pseudosyndactyly (Fine, 2005), muscle contractures that restrict movement, anemia, esophageal strictures (Fine, 2008), microstomia, obliteration of the oral vestibule, dysphagia, rapid tooth decay, nail deformities, and hair loss. In addition, patients with the severe generalized subtype have an increased lifetime risk (over 90%) (RAC, 2007) of developing aggressive squamous cell

CONFIDENTIAL Page 12 of 75

Final Version 8.0, 29 Oct 2019

carcinoma. 87% die by the age of 45 due to metastatic squamous cell carcinoma (Fine, 2010).

Currently there is no effective therapy for this disease. Nearly 10% of RDEB patients die before the age of 10, almost 40% by the age of 20, and 72% before the age of 30. Death is usually the result of aggressive squamous cell carcinoma, sepsis, or of malnutrition due to an inability or unwillingness to eat due to mouth or esophagus involvement (RAC, 2007).

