# 3.4 Estimated Study Duration

The duration is about 20 months per subject, including the Screening, Wound Monitoring and Treatment Periods. Recruitment is anticipated to take approximately 8 months, resulting in total study duration of approximately 28 months. The end of Treatment Period Visit is scheduled to occur at the end of the 12-month treatment phase. Safety data will continue to be collected by clinic visit or telephone contact approximately every 1 year for at least 15 years after the treatment phase.

CONFIDENTIAL Page 19 of 75

Final Version 8.0, 29 Oct 2019

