## 7.5 Long-Term Follow-Up Period

Upon completion of the End of Study / Early Termination Visit, subjects will enter into the Long-Term Follow-Up Period.

#### 7.5.1 Years 1 - 5

At a minimum, subjects will be contacted yearly for at least 5 years. Subjects will be contacted by phone. In addition, the subject's primary care provider will be asked to contact the Investigator regarding any unexpected or serious adverse events. Telephone contact reports will document the discussions and the information obtained will be captured on case report forms. The following activities will occur at the one-year follow-up intervals:

- Collection and analysis of blood sample for RCL testing (can be done remotely).
  - If all post-treatment assays are negative during the first year (e.g., Weeks 4, 12, 16, 25, 32, and 52), collection of the yearly follow-up samples will be discontinued.
- Recording of exposures to mutagenic agents and other medicinal products
- Recording of any new serious adverse events, hospitalizations, or illnesses (including new malignancies, new incidence or exacerbation of a pre-existing neurologic disorder, new incidence or exacerbation of a prior rheumatologic or other autoimmune disorder, new incidence of a hematologic disorder).
- Discussion with primary care provider regarding medication and medical history.
- If a skin cancer occurs in the region of the FCX-007 administration, attempts will be made to collect samples of the skin cancer to evaluate cells for the presence of viral vector.

#### 7.5.2 Years 6 - 15

Subjects will continue to be followed-up on an annual basis for at least 15 years following FCX-007 administration. Follow-ups from years 6 to 15 include:

- Collection and analysis of blood sample for RCL testing (can be done remotely).
  - If all post-treatment assays are negative during the first year (e.g., Weeks 4, 12, 16, 25, 32, and 52), collection of the yearly follow-up samples will be discontinued.

CONFIDENTIAL Page 37 of 75

FI-EB-001 RDEB Phase I/II Protocol

Final Version 8.0, 29 Oct 2019

- Recording of exposures to mutagenic agents and other medicinal products
- Recording of any new adverse events, hospitalizations, or illnesses (including new malignancies, new incidence or exacerbation of a pre-existing neurologic disorder, new incidence or exacerbation of a prior rheumatologic or other autoimmune disorder, new incidence of a hematologic disorder).

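### Long-term events, including malignancies to Year 15, have no analysis that accounts for observation time: Section 14.7.1 gives only counts of entries and patients by phase

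*Combined protocol and SAP*

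**What the plan says.** Safety is the primary objective (2.2.1). The synopsis, under Safety Evaluations, includes delayed adverse events and "Any new malignancies to Year 15". Section 7.5 provides yearly contacts, and 13.2 requires deaths during long-term follow-up to be reported.

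The matching analysis text is short. Section 14.7 states: "Summary statistics for categorical variables will include frequency counts and percentages". Section 14.7.1 states: "Adverse events will be grouped into pre-treatment adverse events and treatment-emergent adverse events", tabulated for each study phase, and then: "The number of adverse event entries, as well as the number of patients will be reported". No closing date for treatment-emergent is given. The opening of Section 14 defines treatment visits as Visits 3 to 10 plus unscheduled visits. Section 14.9 addresses missing data for efficacy only.

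On the length of follow-up, the synopsis and 3.1 say: "The Long-Term Follow-Up is a 15-year period following Week 52/ET in which safety is monitored". Section 3.4 says "for at least 15 years after the treatment phase". Section 7.5.2 says: "Subjects will continue to be followed-up on an annual basis for at least 15 years following FCX-007 administration".

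Section 1.1 gives RDEB mortality as nearly 10% before age 10, "almost 40% by the age of 20, and 72% before the age of 30". It also attributes 87% mortality by 45 to metastatic squamous cell carcinoma, directly after a sentence on the severe generalized subtype.

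**The concern.** The product carries an integrating vector, and the protocol follows subjects for 15 years and tests skin cancers in the treated region for vector. A reader will want to know how much observation stands behind any statement about late malignancy. A count of patients over the number treated cannot show this. A subject lost in Year 2 and one seen cancer-free at Year 15 both sit in the denominator as one patient without an event.

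Three uses of the data are affected:

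- **Losses.** Each lost subject stays in the denominator, while any later malignancy never reaches the numerator.
- **Reports before Year 15.** Section 14.8 foresees yearly safety evaluation, and 3.4 puts the study at about 28 months before long-term follow-up is complete.
- **Comparison of phases.** Phase I subjects are treated first, so at any data cut they tend to have been watched longer, yet events are tabulated by phase without time at risk.

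**Working it through.** The plan gives no figure to reproduce: 14.1 says no formal sample size calculation was made. The check therefore asks how much observation time the protocol's own figures imply, and when a crude proportion goes wrong.

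**1. Inputs (Section 1.1).** Survival S(10) = 0.90, S(20) = 0.60, S(30) = 0.28, S(45) = 0.13. The last value takes the 87% figure as all-cause and applies it to all subjects, which is an assumption. Up to 12 subjects (3.3, which also allows one more in Phase II). Entry ages are not stated, so several are tried.

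**2. Hazards, constant within each interval (assumption).**
- Ages 10–20: ln(0.90/0.60)/10 = 0.0405 per year
- Ages 20–30: ln(0.60/0.28)/10 = 0.0762
- Ages 30–45: ln(0.28/0.13)/15 = 0.0511

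Entry at 7 also uses the 0–10 hazard, ln(1/0.90)/10 = 0.0105.

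**3. Fifteen-year mortality and expected time.** Mortality from entry age a is 1 − S(a+15)/S(a). Expected years observed is the integral of S(a+t)/S(a) over t from 0 to 15. For age 25:
- Mortality: S(25) = 0.410 and S(40) = 0.168, so 1 − 0.168/0.410 = 59%.
- Time: (1 − e^(−0.381))/0.0762 + e^(−0.381) × (1 − e^(−0.511))/0.0511 = 4.16 + 5.35 = 9.51 years.

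**4. Upper limit with zero events.** The upper end of the exact two-sided 95% Poisson interval is −ln(0.025) = 3.689 events, divided by person-years (PY).

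| Entry age, all 12 | Die within 15 y | Years each | PY for 12 | Upper limit per 100 PY |
|---|---|---|---|---|
| No deaths (nominal) | 0% | 15 | 180 | 2.05 |
| 18 | 63% | 9.57 | 115 | 3.2 |
| 20 | 64% | 9.06 | 109 | 3.4 |
| 25 | 59% | 9.51 | 114 | 3.2 |
| 30 | 54% | 10.47 | 126 | 2.9 |
| 7 | 45% | 12.12 | 145 | 2.5 |

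A mix of six aged 7 and six aged 25 gives 6 × 12.12 + 6 × 9.51 = 130 PY and a limit of 2.8.

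**5. Does death bias the crude proportion?** Take assumed hazards of 0.03 per year for malignancy, 0.065 for death and λ for loss. The expected crude proportion by Year 15 is 0.03/(0.095 + λ) × [1 − e^(−15(0.095 + λ))].
- λ = 0: 0.316 × (1 − e^(−1.425)) = 0.240, which is exactly the cumulative incidence with death competing.
- λ = 0.05: 0.183
- λ = 0.10: 0.146

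So death does not bias the proportion; loss does. In 12 subjects these are 2.9, 2.2 and 1.7 expected patients with a malignancy.

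**6. Early report, no losses.** At 5 years the same formula gives 0.316 × (1 − e^(−0.475)) = 0.119, about half the Year-15 value. It is a correct 5-year risk, but a bare count does not say that it covers 5 years.

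**7. Unequal follow-up on the plan's own timetable.** Section 3.4 gives 20 months per subject, of which 12 follow treatment, so about 8 precede it. With 8 months' recruitment, at month 28 the first subject has 28 − 8 = 20 months since first dosing and the last has 12.

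**The case against.** The strongest reply is that, if every subject is followed to death or Year 15, the crude percentage already is the cumulative incidence with death competing. That is correct (step 5). A reader might infer from the high mortality that the planned Year-15 percentage is biased; the arithmetic does not support it. What stands is that Section 14 neither ensures complete follow-up nor shows its extent.

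The mortality figures are also limited. The 87% figure follows text on the severe generalized subtype, no upper age limit is set, and Phase II admits children from 7. Many of the deaths before 45 would themselves be malignancies, so high mortality with no malignancy is an unlikely pairing in that subtype. All this stands: the table shows lost observation time and does not forecast the trial. Holding the 20–30 hazard constant beyond 30 would give 68% mortality from age 25, but it ignores the age-45 figure in the same section.

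A reader might also see two conflicting starts for the 15 years. The documents do not conflict: 7.5.2 sets a minimum counted from administration, and 15 years counted from Week 52 or the end of treatment meets it. This is loose wording.

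Finally, the plan does not say that long-term malignancies enter the 14.7.1 table. They fall there by default, because no other analysis is described. If they were excluded, they would have no analysis at all. Cancers in the treated region are examined individually for vector (7.5.1, 11.1.1, 11.4), which serves causality but gives no rate.

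**Conclusion.** The point holds as a gap in the analysis of long-term safety, and it should be corrected. Long-term events have no stated summary beyond counts and percentages by phase, so losses and reports before Year 15 would make late risk look smaller than it is, and the phases could not be compared.

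For 12 adults entering at 18, 25 or 30, expected observation is about 114–126 person-years rather than 180, and the zero-event upper limit is 2.9–3.2 rather than 2.05 per 100 person-years. Entry near 20 gives 109 and 3.4; enrolling children moves the figures back towards the nominal ones.

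These sizes rest on constant hazards within age bands, on applying the age-45 figure to all subjects, and on entry ages that the documents do not give. One part needs no interpolation: from age 20, the stated figures imply that 1 − 0.28/0.60 = 53% die within 10 years. The hazards for malignancy, death and loss in the bias check are assumed values. The gap itself depends on none of these.

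**What to change.** In 14.7.1:

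- Tabulate events through Week 52 separately from long-term follow-up, and say where the treatment-emergent period ends.
- For malignancies and other long-term events, list for each subject the time from first FCX-007 administration to the event, death or last contact.
- Report total person-years and the rate per 100 person-years with an exact Poisson confidence interval, overall, with person-years also shown by phase.
- State first administration as the time origin for these analyses.

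With 12 or 13 subjects no model is needed. Cumulative incidence curves by phase, at about six subjects each, would be a matter of preference. Aligning the 15-year wording in the synopsis, 3.1, 3.4 and 7.5.2 is an optional clarification.

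The dates should already be available from event recording, the yearly contacts and the reporting of deaths, so no visit or procedure changes. The cost is slightly more analysis and a less favourable stated upper limit on late risk.
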